### 3. No devices will be used.

Use Shift+Return to add line breaks.

### 13.0 Study Timeline (optional)

## 14.0 ClinicalTrials.gov Information

**Directions: If this study has been registered on ClinicalTrials.gov, provide the ClinicalTrials.gov identifier and the investigator/sponsor responsible for registering. If this study has not been registered on ClinicalTrials.gov, provide the rationale as to why and if/when it will be. If it does not meet the requirement for being registered on ClinicalTrials.gov, please state that.**

This study does not meet the requirement for being registered on clinicaltrials.gov

## 15.0 List of Data to be Collected

1. *Indicate what identifiers you will collect*

- Name
- Address (e.g., Zip code, other geographical designation, etc.)
- Dates related to an individual (e.g., Date of admission, birth, surgery, etc.)
- Telephone number
- Fax number
- Email address
- Social security number
- Medical record number
- Health plan beneficiary number
- Account number

- Certificate/license number
- Any vehicle or other device serial
- Device identifiers or serial numbers
- Web URL
- Internet protocol (IP) address
- Finger or voice prints (*includes audio recordings*)\*
- Photographic images (*includes video recordings or CTs or MRIs of heads*)\*
- Other: Any characteristic that would uniquely identify the individual  
 If other, please explain: [Click here to enter text.](#)
- None

\*-Please note, audio or video recordings on smart phones is not allowed. Devices must be encrypted.

2. List all other data to be collected for the research study. Attach all data collection tools on the Local Site Documents page of the SpartaIRB smart form (Other Attachments).
  1. 8 post-class surveys per participant
  2. 2 Perceived Stress Scale per participant
  3. 2 USDA Food Security Screeners per participant
  4. 2 FLEW assessments per participant and food waste tracking logs
  5. 4 24-hour dietary recalls per participant
  7. Data from 2 semi-structured focus groups

## 16.0 Online Data Collection

- We will not collect data through an online platform.

1. List the online platform to be used. The preferred platforms are REDCap and Qualtrics, as these provide good data security and have options for collecting data without individually identifiable information.  
 The weekly post-class surveys, baseline and post intervention assessments will all utilize the platform Qualtrics. The two focus groups will be conducted via CWRU Zoom. Participants can join either via mobile phone or computer. REDCap will be used to schedule participant dietary recall interview in order to keep phone numbers secure.
2. If your intent is to collect the data without identifiers linked to an individual (including IP addresses), describe how you will ensure that no identifiable information will be associated with the data.
  - Qualtrics: enable Anonymize Responses setting (removes IP addresses and location data)
  - REDCap: use of the Public Survey Link
  - REDCap: use of a Participant List without a Participant Identifier field  
(Note: this does maintain a connection between the data and the individual, but it is only accessible to REDCap support personnel and not the researchers. Data collected in this manner should not be referred to as anonymous, but rather as data that is deidentified to the researchers).

Other: REDCap will be used internally to record participant phone numbers and dietary recall information

## 17.0 Data Analysis Plan

**Directions: Describe the data analysis plan, including any statistical procedures. If applicable, provide a power analysis, and study/safety endpoints.** Descriptive statistics of Likert scale weekly class survey questions and thematic analyses of weekly survey open-ended questions and focus groups will be used to assess participant perspectives of the pilot study. Classroom observation notes will be used to determine whether the Nourish and intervention is delivered as intended. Feasibility of recruitment and retention will be based on the number of participants recruited and retained through to completion of post-intervention assessments. In addition, we will analyze the pilot data collected. A series of one-way analysis of covariance will be conducted to determine statistically significant differences at post-intervention between the intervention and delayed intervention control groups on each outcome variable, controlling for the pre-treatment assessment scores on the variable analyzed. Outcome variables consist of total volume of food waste, FLEW assessment scores, food security, perceived stress, and diet quality as assessed by the Dietary Inflammatory Index.

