## 2.0 Objectives

**Directions: Describe the purpose, specific aims or objectives. Be sure to also include the hypothesis being tested.** The purpose of this study is to pilot a culinary nutrition and food literacy intervention entitled Nourish and its corresponding evaluation components to evaluate their feasibility and engage participants in the re-design of the intervention following completion of the Nourish pilot. Specifically, we aim to:

1. Determine whether the Nourish intervention is delivered as intended in terms of time use and objectives delivered.
2. Determine the feasibility of the recruitment, retention, evaluation, and participant engagement methods.
3. Assess participant perspectives on the Nourish intervention so they can be leveraged to re-design the intervention to ensure they are culturally and socially relevant.

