## 3.0 Background

**Directions: Describe the relevant prior experience and gaps in current knowledge describing how this study will add to existing knowledge. Include any relevant preliminary data.** Currently, 12.8% of Americans experience food insecurity (1), and food insecurity is associated with elevated perceived stress (2-3). Food literacy is proficiency in food related skills and knowledge, including food preparation and cooking skills, basic nutrition knowledge, and the ability to prevent food waste. Recent research conducted in Australia suggests that food literacy interventions are associated with improved food security (4). Traditionally food literacy interventions take a recipe-based approach to culinary nutrition and lack information about key components of food literacy, such as food storage and food waste reduction techniques. However, recent research by the PI contends that recipes may be difficult for food insecure individuals to implement at home, given the challenge of procuring ingredients (5), suggesting the need for a new approach. In addition, food insecure households face additional environmental challenges, such as owning fewer cooking utensils, compared to food secure households (6). Based on the Social Cognitive Theory, the Nourish intervention addresses these

limitations by incorporating food waste reduction, food storage knowledge, and improv cooking skills (cooking with what you have on hand) into food literacy and culinary nutrition education, as well as providing key cooking utensils. Eventually, our team plans to test the impact of the Nourish intervention on food literacy, perceived stress, diet quality and food security to determine if food literacy interventions can positively impact perceived stress, diet, and food security. The present pilot study will test the feasibility and acceptability of the Nourish intervention and corresponding evaluation, as well as provide participant feedback on the intervention.

*Please add relevant references at the end of the protocol, not at the end of this section.*

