**E.g., "We will enroll 25 subjects at CWRU and plan to enroll 150 subjects study wide."**

The target sample for Nourish is 40 participants. Twenty participants will receive the intervention immediately. An additional 20 participants will be in the delayed intervention control group. The upper limit is also 40 due to space constraints and small-group educational activities. This is not a multi-site study.

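### Section 17.0 gives statistical significance on five outcomes as the only purpose of the group comparisons in a pilot with no efficacy aim; exploratory adjusted differences with 95% CIs would fit better.

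*Combined protocol and SAP*

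**What the plan says.** Section 2.0 describes a pilot of the intervention and "its corresponding evaluation components to evaluate their feasibility and engage participants in the re-design of the intervention". Its three aims are fidelity of delivery, feasibility of the study methods, and participant perspectives. The second aim reads "Determine the feasibility of the recruitment, retention, evaluation, and participant engagement methods".

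Section 3.0 separates this study from a later one. On the present study: "The present pilot study will test the feasibility and acceptability of the Nourish intervention and corresponding evaluation". On the later one: "Eventually, our team plans to test the impact of the Nourish intervention on food literacy, perceived stress, diet quality and food security".

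Section 5.0 sets 20 participants per group and 40 in total, and explains the cap: "The upper limit is also 40 due to space constraints and small-group educational activities".

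Section 17.0 first covers the survey, observation, recruitment and retention summaries that serve the aims. It then turns to outcomes with "In addition, we will analyze the pilot data collected", followed by "A series of one-way analysis of covariance will be conducted to determine statistically significant differences at post-intervention", comparing the immediate and delayed groups with adjustment for the baseline value of the same variable. The list is: "Outcome variables consist of total volume of food waste, FLEW assessment scores, food security, perceived stress, and diet quality", the last measured by the Dietary Inflammatory Index. The section states no alpha, primary outcome, multiplicity rule, power, exploratory label or confidence interval.

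**The concern.** The four outcomes whose impact test section 3.0 assigns to later work reappear in section 17.0, with food waste added, as outcomes to be tested for significance now. Nothing in the aims calls for that, and the sample size was not chosen for it.

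What is at stake is how the results are read. With five tests in about 40 people, one significant result could be taken as evidence of impact. A non-significant result on, say, perceived stress could be taken as a reason to drop that outcome from the later trial. Unless effects are large, the data would be weak support for either reading. The quantities that would help plan the later trial (adjusted difference with its interval, SD, correlation between baseline and follow-up) are not promised.

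**Working it through.** **Inputs from the documents.** 20 per arm (section 5.0); ANCOVA adjusting for baseline, five named outcomes (section 17.0); data of withdrawn participants removed (section 23.0), so withdrawals reduce the number analysed.

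**Assumed, because the documents give no figure.** Two-sided alpha 0.05 per test; baseline/follow-up correlation r of 0, 0.5 and 0.7; true differences of 0.5 and 0.8 SD; 20 or 16 analysed per arm (16 is a 20% loss); equal correlation between outcomes, from 0 to 0.9; independent participants except in step 4.

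The plan gives no power or precision figure to reproduce. Its 20 + 20 = 40 is consistent.

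**1. At least one false positive in five tests, if no outcome truly differs.** For independent outcomes: 1 − 0.95^5 = 0.226. Simulating correlated normal test statistics gives about 21% at between-outcome correlation 0.3, 18% at 0.5, 15% at 0.7 and 10% at 0.9. A simulation of the ANCOVAs themselves with 20 per arm agrees to within about half a percentage point (20.8%, 18.6%, 15.3% and 10.6%).

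**2. Precision.** In outcome SD units, the standard error is √[(2/n)(1 − r²)] and the 95% half-width is t(0.975, 2n − 3) times that. Example with n = 20 and r = 0.5: √(0.1 × 0.75) = 0.274, times t(37) = 2.026, gives 0.55 SD.

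**3. Power.** Noncentral t with 2n − 3 degrees of freedom and noncentrality d divided by the standard error. Example with n = 20, r = 0.5 and d = 0.5: 0.5/0.274 = 1.83, power 43%.

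| | r = 0 | r = 0.5 | r = 0.7 |
|---|---|---|---|
| Half-width, 20 per arm (SD) | 0.64 | 0.55 | 0.46 |
| Half-width, 16 per arm (SD) | 0.72 | 0.63 | 0.52 |
| Power for 0.5 SD, 20 per arm | 34% | 43% | 58% |
| Power for 0.5 SD, 16 per arm | 28% | 35% | 48% |
| Power for 0.8 SD, 20 per arm | 69% | 81% | 93% |
| Difference with 80% power, 20 per arm (SD) | 0.91 | 0.79 | 0.65 |

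**4. Level of a single test.** With independent participants each test keeps its 5%. Section 12.0, however, has participants cook in small groups and share a group chat, and at the week-12 assessment only the immediate group has had classes. Suppose, for illustration, one class of 20 with intraclass correlation ρ in the baseline-adjusted outcome. The true variance of the difference is then proportional to 2 + 19ρ, while ANCOVA estimates about 2 − ρ. At ρ = 0.02 the ratio is 2.38/1.98 = 1.20, so the critical value 2.026 acts like 2.026/√1.20 = 1.85, an error of about 7%. At ρ = 0.05 the ratio is 2.95/1.95 = 1.51 and the error about 11%. The documents give no intraclass correlation, so this shows only the direction and possible size.

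**The case against.** The best defence is that the plan already frames these analyses modestly. The aims exclude efficacy, section 3.0 defers it, and the ANCOVAs come after the feasibility analyses as an addition. The second aim covers feasibility of the evaluation, so rehearsing the intended model is in scope. All of this stands, and it is why the models should stay. It does not settle how the results will be read, because determining significance is the only purpose the sentence gives.

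It is also fair to say that no harm follows unless someone misreports. A reader might infer that the pilot will judge the intervention, or decide on a later trial, by p-values. The documents do not support that: no go/no-go criterion, decision or efficacy claim is attached to a test.

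A reader might also count more than five tests because FLEW scores are in the plural. The same section uses a plural for the baseline scores on a single variable, and how FLEW is scored is not described, so five is the count that the text supports.

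Thirdly, power is not low for every effect. At 0.8 SD with 20 per arm it is 69% to 93%. That limits the size argument but not the mismatch with the aims.

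Finally, a 95% CI read only for whether it excludes zero is the same 5% test. Adding intervals is therefore not enough; the text must also say how they will be used.

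**Conclusion.** The point holds as a mismatch between the purpose given for the outcome comparisons and the study's aims and size. The mismatch itself rests on the text alone and needs no assumed figure. It is worth correcting but is confined to the added comparisons: the feasibility aims, the ANCOVA model and the sample size for those aims are not in question.

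The size depends on assumptions. At two-sided 0.05 with independent participants and no true differences, the chance of at least one false positive is 22.6% for independent outcomes, about 18% at between-outcome correlation 0.5 and 10% at 0.9. For a 0.5 SD difference, power runs from 28% (16 per arm, r = 0) to 58% (20 per arm, r = 0.7), so the size concern applies to small and moderate effects. If outcomes correlate within a class, the error of a single test could exceed 5%.

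A reader might go further and call the pilot underpowered or too small. That does not follow: it was not sized to detect effects and does not claim to be.

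**What to change.** In section 17.0, replace the clause that gives significance as the purpose with wording such as:

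> For each outcome we will report the baseline-adjusted difference between groups (ANCOVA) with its 95% CI, and, for outcomes analysed as continuous scores, the SD and the baseline/follow-up correlation. These are exploratory estimates to inform a later trial; intervals are not adjusted for multiplicity and will not be used to claim efficacy or lack of it.

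The restriction to continuous scores is there because the documents do not say how food security will be scored. If p-values are kept for inference, state alpha and apply Holm across all outcomes tested.

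The cost is small: a short rewording, with the same data, models and number of participants, and a few more columns in the results table. The downside is that no significant result can be claimed from the pilot.

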## 12.0 Study Design/Procedures

### Directions:

- 1) **Describe the overall study design (e.g.: single visit, single-blind, double-blind, non-randomized, randomized, blood draw, investigational drug, device etc.).**
- 2) **Provide a description of all study-related research procedures being performed, including the length of time involved.**
- 3) **Include procedures being performed to monitor research participants for safety or minimize risks.**
- 4) **Describe the source records including medical or educational records, which will be used to collect data about subjects.**
- 5) **Include a description of any device being used to collect data (e.g., eye tracker, step counter). If the device itself is being studied, include additional information in Section 29.**

1. The study follows a randomized controlled trial with a delayed intervention control design. The immediate cooking class group will receive their intervention in week 3 of the study, and the delayed cooking class group will receive their intervention in week 13 of the study.

2. *Baseline assessment meeting:* Regardless of randomized group, all participants will attend this meeting in week 1. Participants will come to a branch of the Cleveland Public Library to sign their consent form and complete the survey portion of their baseline assessment, consisting of Percieved Stress Scale, USDA Food Security Screener, and the Food Literacy, Environment, and Waste (FLEW) assessment which will be conducted via Qualtrics on tablets provided by the researchers. Two aspects of the baseline evaluation will be conducted after the baseline meeting: a) a series of two 24-hour dietary recalls (via phone calls) lasting approximately 30 minutes each and b) participants will be asked to weigh and log their food waste for one week. During the baseline assessment meeting, participants will be asked to share their phone number and participants will be given a kitchen food scale and waste log. They will be asked to return the log on the first day of class. Additionally, participants will be told what they can expect to happen at each Nourish class and will be coached on how to sign up for GroupMe to receive out-of-class information about Nourish. The duration of the baseline assessment meeting will be

approximately 60 minutes, and will occur two weeks before the immediate cooking classes group's 8-week Nourish class sessions begin.

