*Weekly Nourish classes:* Each Nourish class will last 90 minutes, and will run for 8 consecutive weeks, with one class per week. The immediate cooking class group will receive the Nourish classes in weeks 3-10, and the delayed intervention group will commence the Nourish intervention in weeks 13-20 (after the second intervention assessment period is complete).

Nourish will be held in the teaching kitchen at Dave's Market or CornUcopia. Each class will involve brief instructional video clips, hands-on cooking and tasting experiences. Participants will work individually and as part of small groups during instructional sessions. At the end of each class, participants will receive a grocery bundle and a kitchen gadget that serves both as an incentive and implementation support to promote improved cooking frequency and confidence. Participants will be asked to post photos of what they made with their groceries to the GroupMe, and we will encourage them to engage with fellow classmates on the GroupMe to encourage social support of cooking. Participants will earn raffle tickets for each time they post to the GroupMe and attend a class. A raffle drawing for a pressure cooker will be done at the second-assessment meeting (week 12) for the immediate cooking class group and at the last Nourish class for the delayed group (week 20).

The delayed intervention group will commence the Nourish intervention after the post-intervention assessment period is complete (in weeks 13-20).

A research assistant will attend each class to observe time use and lesson objectives covered.

*Second assessment meeting:* Participants will come to a branch of the Cleveland Public Library to complete their post assessment, consisting of PSS, USDA Food Security Screener, and the FLEW, as well as their return food waste log. Additionally, participants will be encouraged to enroll in an optional focus group series to provide feedback on Nourish. The duration of the second-assessment meeting will be approximately 35 minutes, and will occur in Week 12.

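### The week-12 ANCOVA makes no allowance for shared classes in the immediate arm, so its standard errors and p-values will be too small if outcomes correlate within class

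*Combined protocol and SAP*

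**What the plan says.** Section 12.0 describes the design: "The study follows a randomized controlled trial with a delayed intervention control design". Section 5.0 gives the arm sizes: "Twenty participants will receive the intervention immediately" and "An additional 20 participants will be in the delayed intervention control group".

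In Section 12.0 the immediate arm attends one 90-minute class a week in weeks 3 to 10, in one of two named teaching kitchens. Delivery is in groups: "Participants will work individually and as part of small groups during instructional sessions". Contact between classmates outside class is part of the intervention: "we will encourage them to engage with fellow classmates on the GroupMe to encourage social support of cooking". The second assessment is in week 12, and "the delayed intervention group will commence the Nourish intervention in weeks 13-20", so controls have had no class when the arms are compared.

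For the analysis, Section 17.0 states: "A series of one-way analysis of covariance will be conducted to determine statistically significant differences at post-intervention". The only adjustment is "controlling for the pre-treatment assessment scores on the variable analyzed". The five outcomes are food waste, FLEW scores, food security, perceived stress and diet quality. No class or kitchen term, random effect, robust standard error or ICC appears anywhere. The Section 15.0 data list does not include class group or kitchen, and the number of classes into which the immediate arm is split is not given.

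**The concern.** People who learn and cook together, and who are encouraged to support each other between classes, may have outcomes that move together. By week 12 this can have happened in the immediate arm only. A one-way ANCOVA treats every participant as an independent observation. With positive within-class correlation, the mean of the immediate arm is less precise than the model assumes, and the residual variance is also slightly underestimated. Both errors make the reported standard error too small.

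At stake is how the five comparisons are read. Section 17.0 commits to testing them for statistical significance, and Section 3.0 says the team plans a later test of impact on several of the same outcomes. Nominal p-values and intervals could look firmer than the design supports.

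**Working it through.** The plan states no power, alpha, effect size, standard deviation or ICC, so it has no figure of its own to reproduce. The check asks how far the reported standard error would be from the true one.

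**Inputs from the documents**
- n = 20 per arm (Section 5.0).
- Classes in the immediate arm only at week 12 (Section 12.0).
- Model terms: arm and baseline score (Section 17.0).

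**Assumptions**
- Class size m: one class of 20, two of 10, four of 5 or five of 4.
- ICC of the baseline-adjusted outcome within class: 0.02, 0.05, 0.10.
- Equal total variance σ² in both arms, and a two-sided 5% test.
- For the simulation, baseline correlation 0.5.

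**Formulas**
1. True variance of the arm difference: (σ²/n)[1 + (m−1)ICC] + σ²/n = (σ²/n)[2 + (m−1)ICC].
2. The ANCOVA takes 2s²/n, where the expected value of s² is σ²[1 − ICC(m−1)/(2(n−1))].
3. Ratio of true to reported standard error: sqrt{[2 + (m−1)ICC] / [2 − ICC(m−1)/(n−1)]}.

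**Numbers at ICC 0.05**
- One class of 20: sqrt(2.95/1.95) = 1.23.
- Two of 10: sqrt(2.45/1.976) = 1.11.
- Four of 5: sqrt(2.20/1.989) = 1.05.
- Five of 4: sqrt(2.15/1.992) = 1.04.

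At ICC 0.10 with one class of 20 the ratio is sqrt(3.9/1.9) = 1.43.

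Type I error was simulated for the planned ANCOVA (t-test on 40 − 3 = 37 degrees of freedom, 40,000 trials per cell). The simulated standard-error ratios agree with the closed form to within 0.015 in every cell below. Each cell gives the closed-form ratio and then the type I error.

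| Classes in immediate arm | ICC 0.02 | ICC 0.05 | ICC 0.10 |
|---|---|---|---|
| One of 20 | 1.10; 7.3% | 1.23; 10.6% | 1.43; 16.3% |
| Two of 10 | 1.05; 6.1% | 1.11; 7.7% | 1.22; 10.4% |
| Four of 5 | 1.02; 5.4% | 1.05; 6.2% | 1.10; 7.5% |
| Five of 4 | 1.02; 5.3% | 1.04; 5.9% | 1.08; 6.8% |

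At ICC 0 the ratio is 1.00 and the error rate is 5%.

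**Effect on information at ICC 0.05.** The effective size of the immediate arm is 20/1.95 = 10.3 (one class), 20/1.45 = 13.8 (two) or 20/1.15 = 17.4 (five). The difference detectable with 80% power, before any gain from the baseline covariate, is 2.80 × sqrt(2/20) = 0.89 SD under independence. It rises to 1.08, 0.98 or 0.92 SD respectively.

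**The case against.** The strongest reply is that the harm is conditional. No ICC is given, nothing shows a positive ICC for all five outcomes, and with classes of 4 or 5 the distortion is small. Section 5.0 gives space limits and small-group work as the reason for the enrolment cap, so small classes are possible. All of this stands, which is why the point is worded conditionally and the small-class rows are shown.

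A second reply concerns what is being tested. Class effects arise after allocation, through the intervention. If Nourish changed nobody's outcome, there would be no class effect and no inflation from this source. The inflated error rates apply when classes do shift outcomes but those shifts average to zero over other classes that might have been run. For the effect of the classes as delivered, the ANCOVA is not invalid on this ground. That also stands and limits the claim to inference beyond these classes.

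A third reply is that this is a pilot. The three aims in Section 2.0 are delivery, feasibility and participant perspectives, and Section 17.0 adds the ANCOVA as a supplement. This lowers the priority, but the plan still commits to significance tests on five outcomes.

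A reader might infer more than the documents support:
- **Biased effect sizes.** Ignoring clustering does not bias the point estimate. The residual variance is low by 0.10 × 19/38 = 5% at worst in the table, and the documents do not say that pilot estimates will size the later trial.
- **An instructor effect.** The documents do not describe class instructors, and the use of video clips points towards uniform delivery.
- **Individual randomisation as a stated fact.** It is the natural reading, but the unit is not spelled out.
- **Forty analysed participants.** Forty is the ceiling, and Section 23.0 removes the assessment data of people who withdraw.

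**Conclusion.** The structural point holds: classes are shared in one arm only at the time of comparison, and the model has no term for it. For any positive within-class ICC, the planned standard errors and p-values are too small. The size is unknown because it depends on two quantities the documents omit. At an assumed ICC of 0.05 the understatement runs from about 4% to 23% across the class sizes considered, with type I error of about 5.9% to 10.6% for inference beyond the classes run. At ICC 0.10 the range is 8% to 43%, and 6.8% to 16.3%. These figures assume 20 analysed per arm, equal class sizes and equal variances.

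It would go too far to conclude that the intervals are certainly too narrow for every outcome, or that the pilot's stated aims are compromised. The first needs a positive ICC that the documents neither give nor rule out. The second is wrong because the feasibility, delivery and acceptability results do not rest on the ANCOVA. This is a proportionate correction to exploratory comparisons.

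**What to change.** In Section 17.0, with the matching entry in Section 15.0:

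1. State the number of classes in the immediate arm, and record each participant's class group and kitchen as classes run.
2. Label the five ANCOVA comparisons exploratory. Beside each interval, report a sensitivity interval with the standard error inflated for assumed ICCs of 0.02, 0.05 and 0.10, using the arm and class sizes actually analysed. For equal arms of n and equal classes of m, the multiplier is sqrt{[2 + (m−1)ICC] / [2 − ICC(m−1)/(n−1)]}. For unequal sizes, let M be the sum of squared class sizes divided by n1, the analysed immediate arm, and let n0 be the control arm. The squared multiplier is then {[1 + (M−1)ICC]/n1 + 1/n0} / {(1/n1 + 1/n0)[1 − (M−1)ICC/(n1+n0−2)]}.
3. If the immediate arm is a single class, state that the arm difference cannot be separated from that class's effect and applies to the class as delivered. No model can recover the class effect in that case.
4. Fit a model with a random class effect in the immediate arm only, with small-sample degrees of freedom, only if there are several classes (for example four or more). Treat its class-variance estimate as imprecise.

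The cost is one paragraph and one or two recorded items. Sample size, main method and participant burden do not change. The downside is wider sensitivity intervals, by up to about 43% in the worst case shown (one class of 20, ICC 0.10).

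### Fitted as named, the Section 17.0 ANCOVA leaves out randomised participants who have a week-12 value but no baseline; the exposure is mainly food waste and diet quality

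*Combined protocol and SAP*

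**What the plan says.** Section 17.0 (Data Analysis Plan) states: "A series of one-way analysis of covariance will be conducted to determine statistically significant differences at post-intervention". Each model compares the immediate and delayed groups, "controlling for the pre-treatment assessment scores on the variable analyzed". The outcomes are listed as follows: "Outcome variables consist of total volume of food waste, FLEW assessment scores, food security, perceived stress, and diet quality", with diet quality scored by the Dietary Inflammatory Index. The section names no analysis set and no handling of missing values.

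Section 12.0 (Baseline assessment meeting) splits the baseline measures. Perceived stress, food security and FLEW are completed at the meeting, "conducted via Qualtrics on tablets provided by the researchers". For the rest: "Two aspects of the baseline evaluation will be conducted after the baseline meeting". These are two dietary recalls by phone and one week of weighing and logging food waste. On the log: "They will be asked to return the log on the first day of class". Section 12.0 (Weekly Nourish classes) starts classes in week 3 for the immediate group and week 13 for the delayed group. The second assessment is in week 12.

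Section 5.0 sets the sample: "Twenty participants will receive the intervention immediately"; "An additional 20 participants will be in the delayed intervention control group". Forty is also the upper limit.

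**The concern.** An ANCOVA on the baseline score has no place for someone without that score, and standard software drops the record without comment. A participant who completes the week-12 food waste log but whose baseline log is lost contributes nothing to the food waste comparison, although the outcome was observed in a randomised person.

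Three things follow.

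- **Precision.** With 20 per arm, each lost participant is 5% of an arm, and the cap of 40 leaves no room to replace them.
- **Different subsets.** Losses would vary by outcome, so the five contrasts could rest on different groups of people.
- **Possible bias for food waste.** If the baseline log is handed in at the first class, controls do so in week 13, ten weeks after the immediate arm (13 - 3) and after their own week-12 assessment. Whether a control has a baseline could then depend on arm and on attendance after randomisation. Excluding people on that basis can bias the comparison as well as widen its interval.

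**Working it through.** **The plan's own figure.** The 40 is 20 + 20 and is justified by space and small-group teaching. There is no power calculation, alpha, effect size or missingness rate to reproduce, so everything below is illustrative.

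**Inputs.** N = 40, 1:1 (Section 5.0). Assumed: correlation r between baseline and week-12 values of 0.5; share m1 = 10% missing at week 12; share m0 = 5% to 30% missing at baseline; the two independent.

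**Numbers analysed.** ANCOVA as named: 40(1 - m0)(1 - m1). Everyone with a week-12 value: 40(1 - m1) = 36.

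**Standard error, relative to complete data with no covariate.**

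- ANCOVA as named: sqrt[(1 - r²) / ((1 - m0)(1 - m1))]
- Missing baseline set to the pooled mean: sqrt[(1 - r²(1 - m0)) / (1 - m1)]

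In the ratio of the two, m1 cancels: sqrt[(1 - r²) / ((1 - m0)(1 - r²(1 - m0)))].

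| m0 | Analysed as named | Analysed with mean fill | SE as named | SE with mean fill | Ratio |
|---|---|---|---|---|---|
| 5% | 34.2 | 36 | 0.937 | 0.920 | 1.02 |
| 10% | 32.4 | 36 | 0.962 | 0.928 | 1.04 |
| 20% | 28.8 | 36 | 1.021 | 0.943 | 1.08 |
| 30% | 25.2 | 36 | 1.091 | 0.957 | 1.14 |

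**Sensitivity to r.** At m0 = 20%, r = 0.3 gives sqrt[0.91 / (0.8 × 0.928)] = 1.11, and r = 0.7 gives sqrt[0.51 / (0.8 × 0.608)] = 1.02. Mean fill therefore gains little when the correlation is high. A method that weights the two groups of participants efficiently, with information per arm n[(1 - m0)/(1 - r²) + m0], does better there. Across r = 0.3 to 0.7 it lowers the SE by about 1-2% at 5% missing, 6-10% at 20% and 9-15% at 30%.

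**Simulation check.** 20 per arm, r = 0.5, true standardised difference 0.8, two-sided 0.05, 8,000 runs, all week-12 values present, baselines missing completely at random. ANCOVA as named is compared with mean fill without an indicator.

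| Baseline missing in each arm | Power as named | Power with mean fill |
|---|---|---|
| none | 0.80 | 0.80 |
| 10% | 0.75 | 0.79 |
| 20% | 0.70 | 0.78 |
| 30% | 0.64 | 0.77 |

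Mean estimates stayed between 0.79 and 0.81, and type I error between 0.045 and 0.054, under both methods. When missingness is completely at random the cost is precision, not bias.

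**Baselines missing only in controls.** This is the pattern that the log-return wording makes plausible. Adding a missing-value indicator here recovers nothing: the indicator fits the mean of the affected controls exactly, so the treatment estimate equals the complete-case estimate (largest difference about 1e-14). When that missingness was also related to the outcome, simulation gave a bias of 0.10 to 0.30 SD for both the named ANCOVA and the indicator version. Mean fill without the indicator kept the precision and cut the bias to 0.08 SD or less. A separate simulated scenario gave 0.41 SD for complete-case and indicator alike, so these sizes depend on how strong the dependence is made.

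**The case against.** The best opposing case has several parts.

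- **The plan states no exclusion.** This stands. A reader might infer that Section 17.0 prescribes a complete-case analysis. It does not: it is silent, and exclusion is the default behaviour of the model it names. The ANCOVA itself is a sound choice.
- **Nothing shows that baselines will often be missing.** This also stands. Three of five baselines are taken on site. The recalls are phone interviews scheduled through REDCap (Section 16.0), and missing one of two need not remove the diet value. Completing the baseline set earns $125 (Section 26.0).
- **The independence assumption is favourable to the point.** People who lose the first log may also miss week 12, and filling a baseline cannot recover them. With 10% missing at each time and full overlap, the gain is zero.
- **No stated aim depends on it.** Section 2.0 lists delivery, feasibility and participant perspectives, and Section 3.0 defers tests of impact to later work. This limits the importance of the point, though the comparisons will still be run.
- **Filling a baseline is not always safe.** A reader might infer that it can never distort a randomised comparison because baseline precedes treatment, or that mean fill and a common-baseline mixed model are interchangeable. Neither holds. The value precedes treatment, but its return may not, and the two methods are different estimators.

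What survives is that the named model discards observed randomised outcomes when a baseline is absent, and that standard methods keep them at almost no cost.

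**Conclusion.** The point holds as a minor improvement to the analysis. Its size rests on an assumed missingness rate: the SE is about 2-4% larger at 5-10% missing baselines and about 8-14% larger at 20-30%, with r = 0.5, independent missingness and mean fill as the comparator. It applies mainly to food waste and diet quality.

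For food waste there is also a possible bias, because the log-return instruction, read with the delayed group's class dates, lets log loss differ by arm. A reader might go further and conclude that the food waste comparison is biased. The documents do not support that: the instruction may have been written with the immediate arm in mind, no loss is reported, and bias would need missingness related to both arm and outcome.

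**What to change.** In Section 17.0, state that every participant with a week-12 value is analysed in the group to which they were randomised. Name one method:

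- a two-time-point mixed model with a common baseline mean for both arms; or
- the planned ANCOVA with a missing baseline set to the mean over both arms, without a missing-value indicator.

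Report the number analysed and the number of missing baselines by outcome and arm; in a feasibility pilot those counts are a result in themselves. In Section 12.0, reconcile the log-return instruction with the delayed group's class dates, so that both arms return the baseline log at the same time, before the immediate group's classes begin.

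The cost is a few sentences, trivial programming and slightly more complex reporting, with no new data. Both methods still rely on baseline missingness not depending strongly on arm and outcome together, and this should be said. The change is best made before outcome data are seen. It does not address the removal of withdrawn participants' data under Section 23.0, which is a separate loss.
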